11.5 Please provide a justification for your sample size

There are approximately 1500 deliveries a year at the San Antonio Military Medical Center. Approximately 1100 (73%) of delivered placentas are sent for pathologic examination. Approximately 45% of the placentas are found to have some type of pathology. Given the percentage of placental pathology within this population, 1200 deliveries would be required to compare differences in placental tissue to psychosocial measures with a power of 80% and significance of .05.

11.6 Data Analysis Plan: Complete description: Background, Objectives, Design, Step by Step how the project is going to be done, Data analysis plan:

Data Analysis Plan:

Statistical Analysis System (SAS) version 9.4 will be used for all analyses. Descriptive statistics (mean, sd, median for each continuous variable and proportions for each discrete variable) will be used to describe the sample. Linear or generalized linear mixed models will be developed for all variables, prenatal anxiety, self-esteem, family adaptability/cohesion, prenatal depression and perceived support, as well as the protein and RNA values, in order to examine their association with placental metrics across pregnancy. The linear (mixed) model will be used for all normally distributed continuous data. In the case of skewed continuous outcome data, the generalized linear (mixed) model with gamma distribution and log-link will be chosen. For binary or dichotomized outcomes, a mixed model logistic regression will be chosen. Measurement times (dates of data collection by gestational age), will be included in the models as predictors when available with and without adjusting for the participant's age, employment status, prior deliveries, marital/partner status, education, deployment of partner during pregnancy, military branch of service of participant or partner, ethnicity, military rank of participant or partner and MOPS group. In the case of dual military couples, the rank and service of the active duty woman will be used. The final models will be determined with backward elimination procedure. Timing of data collection (weeks gestation), may also be chosen as a random effect within the model. Additionally, each prenatal variable (prenatal anxiety, self-esteem, depression, family adaptability/cohesion and resilience) will be longitudinally regressed on measurement time to obtain the slope through best linear unbiased predictor (BLUP). The resulted individual slopes will be used to determine any significant effects for prenatal psychosocial scores to pregnancy complications, birth and infant outcomes, and to the physiologic data (both placental scores and biomarker data).

To examine if anxiety mediates the relationship between biomarkers and birth outcomes, we will develop a Baron and Kenny (1986) mediation model assess the relationships as in Bauer and Preacher (2006). We will conduct three mixed regression models adjusted for all appropriate covariates:

1. Regress birth outcome on biomarker.
2. Regress birth outcome on biomarker and anxiety.
3. Regress anxiety on biomarker.

For the above regression models, (1) and (2) will use logistic regression and (3) will use linear or a generalized linear model.

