3) Determine the effect of maternal anxiety on the association between placental molecular changes on pregnancy and birth and infant outcomes.

Hypotheses:

1a) Increased values for measures of prenatal maternal anxiety, stress, and depression will be associated with increased placental pathology.

2a) Increased values for measures of prenatal maternal anxiety, stress, and depression will be associated with increased Th1 response in respect to both Th2 and Th17 immunological response.

1b & 2b) Increased values for measures of prenatal maternal anxiety, stress, and depression will correspond with both increased oxidative stress and general stress hormones.

9.4 Study Design:

Describe study design in one to two sentences (e.g., prospective, use of existing records/data /specimens, observational, cross-sectional, interventional, randomized, placebo-controlled, cohort, etc.). Specify the phase – Phase I, II, III, or IV – for FDA-regulated investigational drug research

The study is a repeated measures, longitudinal design in which Active duty and DoD beneficiary pregnant women, 18 years of age and older, that are currently being recruited and consented for the Mentors Offering Maternal Support (M-O-M-S) research program at the Brooke Army Medical Center (BAMC). They will also be invited to participate in the placental study, as well as pregnant women entering prenatal care in the first trimester, who are not in the M-O-M-S program. Women choosing not to participate in the M-O-M-S study can elect to participate only in the placental study. Psychosocial measures of prenatal anxiety, depression and resilience will be collected at study entry and 12, 16, 24, and 32 weeks gestation. Placentas, of women consented to this study will be obtained following delivery.

No inducements, monetary or otherwise, will be offered to terminate a pregnancy [45 CFR 46.204 (h)]. Individuals engaged in the research will have no part in any decisions as to the timing, method, or procedures used to terminate a pregnancy [45 CFR 46.204(i)]. Individuals engaged in the research will have no part in determining the viability of a neonate [45 CFR 46.204(j)].

9.5 Target Population:

Describe the population to whom the study findings will be generalized

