Women choosing not to participate in the MOPS study can elect to participate only in the Placenta Study.

Date(s):

Upon final approval from the IRB and deferral from the BAMC HRPO, recruitment of participants is anticipated to begin in November 2019 and continue through March 2021. Birth and outcomes data will be retrieved from both the mother's and newborn infant's electronic medical record through December 2021, with the study ending February 28, 2022.

10.2 Data Collection:

Describe all the data variables, information to be collected, the source of the data, and how the data will be operationally measured.

Data Collection and Processing:

For women who have consented to participate in the study, following delivery, all placentas transported to Pathology are placed in a labeled tissue container and "Labor and Delivery Placenta Pathology Submission Form" is attached per normal standard procedures.

The obstetrical provider will place the order for histology, annotating on the order submission that the placenta is designated as a MOPS study placenta for pathologic evaluation. Once the placenta specimens for this study arrive in the pathology laboratory, the appropriate lab research personnel will be notified and the specimen will be given a unique code for study purposes and tissue specific collection will occur. The placenta will undergo the usual examination in accordance with local SOPs. Additionally, unlabeled and coded slides of each case will be processed concurrently and collected by BAMC research personnel. These coded slides will be sent to [name] at UIW for review.

During the gross examination selected portions of the placenta will be taken and flash frozen, in addition to the usual sections taken for histology processing. The placental specimens will be reviewed by [name] for diagnosis based on histology. The flash frozen tissue will then be prepared for shipment to 59 MDW Center for Advance Molecular Detection (CAMD), for the identification of immunological, inflammatory, and hormone biomarkers.

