Pregnancy and neonatal outcome data including gestational age at delivery, infant birthweight, mode of delivery, and pregnancy complications, including pre-eclampsia, gestational hypertension, gestational diabetes, and perinatal and neonatal infections, will be collected from the maternal and infant medical records. If missing from the demographic data form, maternal parity, gestational age at first prenatal appointment, ethnicity, beneficiary status (active duty vs. dependent), smoking history, and other medical history will be obtained from the obstetrical record. The participants have signed a HIPPA form as part of the MOMS study and all data mentioned is being collected as a part of this study.

11.2 Sample Size:

1200

11.3 Total number of subjects requested (including records and specimens):

1200

11.4 If you are recruiting by study arm, please identify the arms of the study and how many subjects will be enrolled in each arm

N/A

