12.4 Special categories, check all that apply

Minors /Children
 Students
 Employees - Civilian
 Employees - Contractor
 Resident/trainee
 Cadets /Midshipmen
 Active Duty Military Personnel
 Wounded Warriors
 Economically Disadvantaged Persons
 Educationally Disadvantaged Persons
 Physically Challenged (Physical challenges include visual and/or auditory impairment)
 Persons with Impaired Decisional Capacity
 Prisoners
 Pregnant Women, Fetuses, and Neonates
 Non-English Speakers
 International Research involving Foreign Nationals - Headquarters Review is necessary

12.5 Inclusion Criteria:

Order Number	Criteria
1	Inclusion: Prima or multigravida; 1 st trimester of pregnancy at consent; \geq 18 years old; wife or DoD beneficiary (Active Duty or retiree) partner to a military service member or retiree or a DoD beneficiary member (Active Duty, retiree). If the pregnant woman is not a DoD or TRICARE beneficiary, than Secretarial Designee (SECDES) status approval must be obtained in order for her to be eligible to participate in the research study, based on DoDI 6025.23.

12.6 Exclusion Criteria:

Order Number	Criteria
1	Exclusion: Anticipated permanent change of station during study; dependent daughter of active duty or retired military member; $>$ 12 weeks gestation at consent; $<$ 18 years of age; inability to understand or speak English; non-sponsored DoD members (civilians).

13.0

Recruitment and Consent

13.1 Please describe the recruitment process, including how subjects will be identified and selected for the study.

The study inclusion criteria includes, being a pregnant woman, in the first trimester, Active Duty or a DoD beneficiary. The women may also be participants in the Mentors Offering Maternal Support study at BAMC. All women attending OB orientation have had their pregnancies verified through the OB clinic. Therefore, additional screening is not required.

Identification of participants will occur in the following ways:

1) Women entering OB care within the first trimester of pregnancy (≤ 12 weeks) will be introduced to the study by research team members in person or by phone. For those women indicating interest in participating they will be provided the study information, a review of the inclusion/exclusion criteria for participation and the informed consent documents.

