Explain the process for withdrawal and specify whether or not the subjects will be given the opportunity to withdraw their data their data/specimens in the event they wish to withdraw from the study

Participants are free to withdraw at any time. The decision to withdraw will not affect subjects' ability to receive medical care and will not be penalized or lose any benefits to which the subject would otherwise be entitled. If a subject withdraws from the study, all the associated data and tissue samples will be destroyed.

14.0 **Risks and Benefits**

14.1 **Risks of Harm:**

Identify all research-related risks of harm to which the subject will be exposed for each research procedure or intervention as a result of participation in this study. Consider the risks of breach of confidentiality, psychological, legal, social, and economic risks as well as physical risks. Do not describe risks from standard care procedures; only describe risks from procedures done for research purposes

There is minimal risk for participating in this study. Personal information (the questionnaire booklets and demographic data) are securely maintained on a password protected computer with a secured study folder. The paper documents will be locked in a file cabinet in the private secured office of the nurse researcher. Only members of the research team, listed on the research protocol, will have any access to the information. The demographic information will be entered into an electronic spreadsheet that is password protected. The data from the questionnaire booklets and the placental tissue data are entered into a computer data program with no identifiable information. This program is also password protected. At the conclusion of the study, all documents will be shredded. The slides and tissue biopsies will be destroyed unless the research subject consents to maintain the placenta tissue and research data in a data/tissue repository.

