The research team will secure the ICD, HIPAA and any study related documents as indicated above. When recruiting, no items will be left unattended, and all consent items will be maintained in envelopes. Participant consents will be scanned into a separate password-protected file from all other study data and submitted to the IRB annually. The paper copies of all the participant consents will be scanned at the study site into a password-protected file, separate from all other study data, and paper copies of participant consents will be shredded. Personal information are securely maintained on a password protected computer with a secured study folder. Documents will be locked in a file cabinet in the private secured office of the nurse program coordinator. Only members of the research team, listed on the research protocol, will have any access to the information. The demographic information will be entered into an electronic spreadsheet that is password protected. The data from the questionnaire booklets and the placental tissue data are entered into a computer data program with no identifiable information. This program is also password protected. At the conclusion of the study, all documents will be shredded.

Participants could experience emotional distress or anxiety that may affect the well-being of themselves or their unborn infant. There may be feelings of isolation, particularly if one's husband/partner is away. It is expected that some participants will have unexpected terminations of their pregnancy. All events that are life-threatening or fatal will be reported within 24 hours. Any other possible adverse events (expected or unexpected) will be reported to the local IRB as well as the governing IRB at BAMC and at the WHASC according to their guidelines.

See section 14.2 for additional information.

14.4 Potential Benefits:

Describe any real and potential benefits of the research to the subject and any potential benefits to a specific community or society

If the individuals in the research are considered experimental subjects (per 10 USC 980), and they cannot provide their own consent, the protocol must describe the intent to directly benefit all subjects

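### Protocol 11.5 requires 1200 deliveries, but 11.2 and 11.3 request only 1200 women consented by 12 weeks, with no allowance for loss

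*Protocol*

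**What the plan says.** Protocol 11.5 gives the sample size requirement in deliveries: "1200 deliveries would be required to compare differences in placental tissue to psychosocial measures with a power of 80% and significance of .05". Its supporting figures are about 1500 deliveries a year at the site and placental pathology in about 45% of placentas. It gives no target difference, standard deviation, test or sidedness.

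Section 11.2 sets the sample size at 1200. Section 11.3 sets the total number of subjects, records and specimens included, at 1200 as well.

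Other sections fix when a woman is counted and what can happen afterwards:

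- **Entry.** Section 12.6 excludes women beyond "12 weeks gestation at consent", and 12.5 and 13.1 likewise place entry in the first trimester.
- **Collection.** Sections 9.4 and 10.1 say: "Placentas, of women consented to this study will be obtained following delivery".
- **Pregnancy loss.** Sections 14.3 and 16.1 say: "It is expected that some participants will have unexpected terminations of their pregnancy".
- **Withdrawal.** Section 13.6 says: "If a subject withdraws from the study, all the associated data and tissue samples will be destroyed".

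No allowance for loss between consent and placenta appears in 11.2 to 11.5 or elsewhere in the protocol.

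**The concern.** The two figures of 1200 count different things. One is deliveries, the unit on which the power statement rests. The other is women who enter months before delivery. They can be equal only if every consented woman stays in the study, delivers and contributes a placenta, and the protocol says that this will not happen.

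A reader of 11.2 to 11.5 will take 80% as the power of a study enrolling 1200 women. The stated justification supports that only with no loss at all, or if 1200 contains a margin that 11.5 does not mention. The enrolment total and its justification are both fixed in this document, so a separate analysis plan could not make 1200 early-pregnancy consents equal 1200 deliveries.

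**Working it through.** **Inputs from the protocol.** Requirement: 1200 deliveries, power 80%, significance .05 (11.5). Subjects requested: 1200 (11.2, 11.3). Pathology in 45% of placentas and 1500 deliveries a year (11.5). Recruitment November 2019 to March 2021, which is 17 months (10.1).

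**Assumptions.** Two-sided test, since sidedness is not stated, and normal approximation. Loss from consent to usable placenta, L, of 5%, 10%, 15% or 25%, since the protocol gives no rate.

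**Can 1200 be reproduced?** No, because 11.5 gives no effect size. It can only be solved backwards. For an unadjusted comparison of a psychosocial score between women with and without placental pathology (45% and 55% of 1200, so 540 and 660):

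d = (1.960 + 0.842) × √(1/540 + 1/660) = 0.163 SD.

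This is an illustration, not the mixed models planned in 11.6.

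**Direction of the shortfall.** Deliveries = 1200 × (1 − L), which is below 1200 for any L above zero. This step needs no assumed rate.

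**Size of the shortfall.** For any effect that 1200 would detect with exactly 80% power:

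- Power after loss = Φ((1.960 + 0.842) × √(1 − L) − 1.960). At L = 15%: 2.802 × 0.922 − 1.960 = 0.623, and Φ(0.623) = 73.3%.
- Increase in effect needed to keep 80% = 1/√(1 − L) − 1. At L = 15%: 1/0.922 − 1 = 8.5%.
- Women needed for 1200 deliveries = 1200/(1 − L), rounded up. At L = 15%: 1200/0.85 = 1412.

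| Assumed loss | Placentas from 1200 women | Power | Effect must be larger by | Women needed for 1200 deliveries |
|---|---|---|---|---|
| 5% | 1140 | 78.0% | 2.6% | 1264 |
| 10% | 1080 | 75.7% | 5.4% | 1334 |
| 15% | 1020 | 73.3% | 8.5% | 1412 |
| 25% | 900 | 67.9% | 15.5% | 1600 |

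In the illustration, the detectable difference moves from 0.163 SD at 1200 placentas to 0.176 SD at 1020.

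**When the loss would not matter.** If the unstated target were 0.18 SD, the number needed at a 45:55 split is (2.802/0.18)² / (0.45 × 0.55) = 979. Then 1200 women could absorb a loss of 1 − 979/1200 = 18%.

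**Enrolling more.** The window holds about 1500/12 × 17 = 2125 deliveries. Taking deliveries as a stand-in for women entering care, 1200 is 56% of them, and 1334, 1412 and 1600 are 63%, 66% and 75%. These last three are upper figures, because they divide women counted before loss by deliveries counted after it. If all loss were pregnancy loss, entrants would exceed deliveries by the same factor (2125/0.90 = 2361, and 1334/2361 = 56.5%) and the share would stay at 56.5%. The true share lies between, before any exclusions.

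**The case against.** The strongest reply is that no loss of power has been shown. Section 11.5 states no difference, so 1200 cannot be reproduced and might already contain a margin; the power series holds only if 1200 is the exact minimum. **This stands as a limit on the conclusion.** It does not remove the mismatch: 11.5 presents 1200 deliveries as what is required and mentions no reserve.

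The loss rates have no source in the protocol, and at 5% the fall is only two points. Section 12.6 also excludes women expecting a permanent change of station, which removes one foreseeable cause of loss. Both points are fair. The fall becomes material at about 10% or more, and the relocation exclusion reaches neither pregnancy loss, nor withdrawal, nor unexpected moves.

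Finally, the first two aims are exploratory and the remedy leaves the conduct of the study unchanged, which argues for modest weight. That is reasonable as to urgency. The protocol nevertheless makes a specific power claim, and the claim should match the number of women it asks for.

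**Conclusion.** The concern holds. As written, the enrolment requested cannot deliver the number that 11.5 calls required, and this follows from the protocol's own text without any assumed rate.

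The size depends on the loss rate. For an effect sitting exactly at the 80% limit with 1200 placentas, power is about 78% at 5% loss and 68% at 25%, under a two-sided test and normal approximation. Whether the study's actual power falls below 80% is open. It does if the target is the smallest effect that 1200 deliveries can detect, and it need not if the target is larger by the percentages in the table. The defect is a wrong statement of what 1200 women provide. It does not show that 1200 women are too few.

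**What to change.** Keep 1200 enrolled. In 11.5, replace the sentence that calls 1200 deliveries required with:

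1. the test and the difference on which 1200 rests;
2. an explicit loss assumption from consent to usable placenta, and the resulting number of placentas (1020 at 15%, for example);
3. the power for that difference, or the difference detectable with 80% power, at that number.

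If 1200 already includes a margin, say so and give the number of deliveries actually needed.

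The cost is a change of text in 11.5, with no extra participants, procedures or analyses. The price is a slightly less favourable quoted power or detectable difference. Raising enrolment to 1334, 1412 or 1600 women (10%, 15% or 25% loss) would also restore 1200 deliveries. It is the costlier route and is hard to justify until the target difference is stated.

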Research efforts in the investigation of reproductive health, especially as it relates to mental health of active-duty servicewomen, female veterans, or wives of service members is limited (Ganzer, 2016). As operational conditions have intensified so has the stress and anxiety experienced by the active duty member and their spouses (Verdeli et al., 2011). As result of these stresses, many veterans are reported to have long-term mental health issues associated with their service. Mental health along with physical condition, socioeconomic status, and the availability of social support can significantly impact pregnancies. As operational stress and anxiety rise for active duty women coupled with lack of necessary social support increases the likelihood of pregnancy complications and poor birth outcomes (Dunkel-Schetter, 2011). To better elucidate the roles of mental health and social support on birth outcomes, it is important to the examine how these psychological factors are manifested physiologically. Although literature has shown that the biopsychosocial mechanisms PTB are driven by an inflammatory/immune response resulting from the activation of the hypothalamic-pituitary-adrenal (HPA) axis, there are limited understanding the mechanisms that leads to LBW. However, it is hypothesized that elevated proinflammatory cytokines and C-reactive proteins (Coussons-Read et al., 2007) that is seen in PTB might also play role in LBW. Conceivably, inflammatory/oxidative stress responses leading to alteration in cellular functions and placental development affects fetal nutrient transport, which ultimately results in lower birth weights. Prospective studies are, in which pregnant women are followed across pregnancy, with repeated measures of anxiety and symptoms of depression are needed to be compared to pathological placental changes and molecular biomarkers associated with poor birth outcomes.

9.3

Objectives/Specific Aims/Research Questions:

Describe the purpose and objective(s) of the study, specific aims, and/or research questions/hypotheses

Purpose of Study:

- 1). Explore the associations of prenatal maternal anxiety to placental histological findings
- 2). Explore the associations between prenatal maternal anxiety and the function of pro-inflammatory, anti-inflammatory, and immunoregulatory cells found in placental tissue.

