11.0 Statistical/Data Analysis Plan

11.1 Statistical Considerations:

List the statistical methods to be used to address the primary and secondary objectives, specific aims, and/or research hypotheses. Explain how missing data and outliers will be handled in the analysis. The analysis plan should be consistent with the study objectives. Include any sub-group analyses (e.g., gender or age group). Specify statistical methods and variables for each analysis. Describe how confounding variables will be controlled in the data analysis

For characterization and identification of specific immunological, inflammatory, and hormone biomarkers changes, placental tissue biopsies taken from the same locations as the tissue for the paraffin blocks, will be flash-frozen in liquid nitrogen prior to being sent (by courier) to the 59th MDW Center of Advanced Molecular Detection (CAMD) at JBSA-Lackland. Once received, each biopsy will be homogenized and divided into two groups for analysis: (1) RT-PCR for RNA expression; (2) Multiplexed panel for protein expression. Response groups will be divided into: (1) Th1, (2) Th2, (3) Hormonal, and (4) Oxidative Stress, and some of their specific factors are summarized in **Table 1**.

Table 1: Select Immunological, Hormonal, and Oxidative Stress Factor for Analysis.

Th1	Th2	Th17 (Treg)	Oxidative Stress	Stress Hormone
IFN-γ	IL-3	IL-17	Hydrogen Peroxide	Prostaglandin E2
TNF-β	IL-4	IL-23	Nitric Oxide Synthase Family	Cortisol
TNF-α	IL-5	TGF-β	S-glutathionylation	CRH (HPA Axis)
IL-12p70	IL-10		C-reactive Protein	ATCH
IL-18	IL-13			DHEA
IL-1β	LIF			
IL-6				
IL-2				
MIP-1α				

Specifically, analysis will explore the physiological correlations between the biomarker groups as a response to psychosocial factors and in relation to histopathological analysis. The psychosocial measures obtained at various timepoints in first, second, and third trimester are presented in Table 2.

Table 2.

Variable	Measurement	Collection Timepoints

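### Section 11.6 lets backward elimination choose the final association models with no term exempt, so listed confounders can be dropped from the result that is called final

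*Protocol*

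**What the plan says.** Protocol section 11.6 (Data Analysis Plan) sets up the association models: "Linear or generalized linear mixed models will be developed for all variables". The list that follows covers the psychosocial scores and the protein and RNA values, and the stated aim is to examine their association with placental metrics across pregnancy.

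Measurement times "will be included in the models as predictors when available with and without adjusting for" a list of covariates. That list holds age and MOPS group together with "employment status, prior deliveries, marital/partner status, education, deployment of partner during pregnancy, military branch of service of participant or partner, ethnicity, military rank": ten in all.

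Soon afterwards comes the rule at issue: "The final models will be determined with backward elimination procedure". The sentence carries no qualification. No term is marked as always retained, and no common adjustment set is named.

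Section 11.1 of the form asks the authors to "Describe how confounding variables will be controlled in the data analysis". The text under 11.1 gives no rule, so for the association models the answer is the 11.6 list and the elimination step that follows it.

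**The concern.** This is a longitudinal observational cohort. Nothing is randomised, so covariate adjustment is the main protection against confounding. Backward elimination judges a covariate by its own partial significance for the outcome. What matters for confounding is how far its removal shifts the exposure coefficient. The two can differ: a covariate clearly related to the exposure but modestly related to the outcome may fail the test and still leave bias behind when it goes.

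Three consequences follow from the rule as written:

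- Listed confounders, including MOPS group, can be dropped from the model that is called final.
- The reported p-values and intervals treat the surviving model as if it had been fixed in advance, so they overstate precision.
- Selection is done model by model, so associations for different scores or markers may be adjusted for different covariates and are harder to compare.

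The purposes are partly exploratory ("Explore the associations of prenatal maternal anxiety to placental histological findings"). However, section 9.3 also states directional hypotheses and section 11.5 works at significance .05, so the adjusted association will be read as a test.

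**Working it through.** **The plan's own figures.** The protocol gives no number for the effect of this rule, so there is nothing to reproduce. Inputs from the protocol are the ten covariates (11.6), n = 1200, 45% pathology and significance .05 (11.5). Expected pathology cases: 1200 × 0.45 = 540. Everything else below is assumed.

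**Step 1: why a real confounder is dropped.** Take a continuous metric with residual SD 1, an exposure A with variance 1, and five independent confounders. Each correlates d = 0.25 with A and has outcome coefficient b = 0.05. A has no true effect.

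- Variance of one confounder given A and the other four: 1 − d²/(1 − 4d²) = 1 − 0.0625/0.75 = 0.917.
- SE of its coefficient in the full model: 1/√(1200 × 0.917) = 0.0302.
- Expected z: 0.05/0.0302 = 1.66.
- Chance that it misses p < .05 in the full model: Φ(1.96 − 1.66) = about 0.62. So about 5 × 0.62 = 3.1 of the five are at risk straight away.

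**Step 2: what the loss does to the exposure.**

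- Dropping one confounder biases the coefficient of A by b × d/(1 − 4d²) = 0.05 × 0.25/0.75 = 0.017.
- Dropping all five biases it by 5 × 0.05 × 0.25 = 0.0625. The SE of A is then about 1/√1200 = 0.029, so the bias is a little over two standard errors.
- A simulation of this setting (elimination at .05, A kept in) dropped 3.4 of the five on average. Mean bias was 0.033 and type I error 30%, against 6% for the full model.
- Over b = 0.03 to 0.10, type I error after elimination was 10-30%. It was 7-14% if A itself could also be eliminated.

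**Step 3: binary pathology, a range of settings.** Logistic model, n = 1200, 45% pathology, no true association. Ten standard-normal covariates, of which 2, 4 or 6 confound. Exposure-confounder coefficient 0.1 (weak) or 0.2 (stronger); confounder log odds ratio 0.08 or 0.12 per SD; exposure kept in; Wald elimination.

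| Setting | Stay level | Type I error after elimination |
|---|---|---|
| 2-6 weakly tied confounders | .05 to .20 | about 4-9% |
| 2 more strongly tied | .05 to .20 | 5-8% |
| 4 more strongly tied | .05 | 8-13% |
| 4 more strongly tied | .157 (AIC-like) | 6-9% |
| 6 more strongly tied, same direction | .05 | 16-20% |
| 6 more strongly tied, same direction | .10 | 11-14% |
| 6 more strongly tied, same direction | .157 | 9-11% |
| 6 more strongly tied, same direction | .20 | 8-9% |
| 6 more strongly tied, mixed directions | .05 to .20 | 8-12% |
| Full model, all ten kept | none | 4-6% |

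An independent repeat with 1000 runs per cell gave 6.0% for two weak confounders, 10.2% for four stronger and 17.2-17.5% for six stronger, all at .05. The full model gave 4.8-5.8% in those cells. For six at .157 and .20 the repeat gave 9.3% and 7.8%. At least one true confounder was lost in 73-100% of its runs.

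**Step 4: the model the other way round.** If the repeated score is the mixed-model outcome (five times, intraclass correlation 0.6 assumed) and pathology the predictor, the range is 4.6-13.5% after elimination and 4.2-5.9% for the full model.

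**Step 5: price of keeping all ten.** The ratio of the full-model SE to the pruned SE was 1.01-1.13. If the ten covariates need about 27 parameters (assumed), cases per parameter are 540/27 = 20. At half the sample it is 270/27 = 10. For a metric with 10% prevalence (assumed, 120 cases) it is 120/27 = 4.4.

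**The case against.** **That no term is exempt is read from silence.** A statistical analysis plan might name forced-in terms or a stay level. This stands in part, and for that reason the missing criterion is not criticised here. But the protocol does fix the method that determines the final models, without qualification, and a threshold would implement that rule, not replace it.

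**A fully adjusted fit is already planned.** True: 11.6 plans fits with and without adjustment. A reader might infer that the full model will go unreported, and the text does not say so. The point is only that the eliminated model is the one called final.

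**The size is driven by assumptions.** Correct. Only 1200 and 45% come from the protocol. The upper figures need several confounders pulling the same way and a strict stay level. The simulated covariates are continuous, whereas most listed ones are categorical. The full model also does well partly because every confounder is assumed to be on the list. Smoking history is collected but not listed, so keeping all ten does not guarantee control of confounding.

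**Hypothesis 2a.** A reader might infer that the contrast in 2a (scores "will be associated with increased Th1 response in respect to both Th2 and Th17 immunological response") is directly undermined because each marker in Table 1 selects its own covariates. The protocol does not securely support that. Section 11.6 ties the mixed models, markers included, to placental metrics. It links psychosocial scores to biomarker data through the individual slopes, in a separate sentence. Nor does it say that every Table 1 factor gets its own model, since markers are also handled as response groups. No claim is made here about 2a, the slope models or the mediation models.

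**Conclusion.** The point holds for the placental-metric association models in section 11.6. The protocol lists ten covariates and then adopts a data-driven rule that can remove any of them from the final model. The direction of harm, residual confounding and understated uncertainty, does not depend on the threshold, though its size does.

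That size cannot be read from the protocol. Inflation is negligible with few weak confounders. In the logistic illustrations it is roughly 8-20% with four to six more strongly tied confounders at a stay level of .05. Looser levels bring it down, to 6-9% for four confounders at .157 and 8-9% for six at .20. Linear settings with five confounders correlated 0.25 with the exposure reached 10-30%. The full model stayed at 4-6% throughout. These figures assume p-value elimination and that the confounders are among the ten listed covariates.

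The exploratory wording of the first two purposes lowers the stakes but does not remove them, given the directional hypotheses. The change is worth making because it is cheap and the better model is already planned.

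**What to change.** In section 11.6, replace the elimination sentence with three statements:

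1. For every placental-metric association model, the main adjusted result is the model that keeps the exposure, measurement time (where the outcome or score is repeated) and all ten listed covariates.
2. The unadjusted model and any backward-eliminated model are shown as secondary only.
3. For a rare binary metric with too few events for all ten, use one reduced covariate set fixed in advance on subject-matter grounds, or a penalised fit, in place of data-driven elimination.

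Measurement time needs to be named as retained. If only the exposure and the ten covariates were protected, time would become the main term open to removal from a longitudinal model.

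Cost: wording only, since all ten covariates are already in the plan. Intervals would be about 1-13% wider than after pruning in the illustrations, with the upper end only for six confounders and the stronger link. At about 20 pathology cases per assumed parameter, or 10 at half the sample, the full set is workable for overall pathology. At about 4 for a metric with 10% prevalence it is not comfortable, which is why the third statement is needed.
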